3.3 Subject enrolment

Investigator(s) should keep a record, the subject screening log, of subjects who entered prestudy screening.

The Investigator(s) will:

- 1. Obtain signed informed consent from the potential subject or their guardian/legal representative before any study specific procedures are performed
- 2. Assign potential subject a unique enrolment number
- 3. Determine subject eligibility. See Section 3.1&3.2

4. Enrol and treat eligible subject

If a subject withdraws from participation in the study, then his enrolment code cannot be reused.

3.4 Procedures for handling incorrectly enrolled subjects

Where a subject does not meet all the eligibility criteria but is incorrectly enrolled and started on treatment, the Investigator should inform the AstraZeneca study team immediately, and a discussion should occur between the AstraZeneca study team and the investigator regarding whether the subject need to withdraw from the study. The AstraZeneca study team must ensure all decisions are appropriately documented.

3.5 Restrictions

Subjects must abstain from donating blood/plasma from the time of informed consent and for 90 days after the last dose of the IP.

Subjects should be willing to use barrier methods of contraception during the study and for 30 days after study, unless their partners are post-menopausal, surgically sterile or are using accepted contraceptive methods.

3.6 Discontinuation of investigational product

Subjects may be discontinued from IP in the following situations:

- Subject decision. The subject is at any time free to discontinue treatment, without prejudice to further treatment
- Adverse Event
- Severe non-compliance with the study protocol

Patients can discontinue the investigational product at any time, without any damage to further treatment. For the patients who determine to discontinue the investigational product, the reason for the discontinuation and the occurrence of any adverse event (AE) should be always inquired. At the same time, investigators can judge if the patient is not suitable to receive the IP based on the condition, and collect the reason for the discontinuation. If the dose of Zoladex (Goserellin acetate implant) is delayed by more than 7 days during on-treatment period, early termination of study treatment will be considered. If Zoladex is permanently discontinued, Casodex should be permanently discontinued. Adverse events will be followed up (see Section 6), and patients should return all the unused investigational product.

3.7 Discontinuation/completion of the study

3.7.1 Screen failures

Screening failures are subjects who do not fulfil the eligibility criteria for the study, and therefore are not allowed to be enrolled.

3.7.2 Withdrawal of the informed consent

Subjects are free to withdraw from the study at any time (investigational product and assessments), without prejudice to further treatment. A subject who withdraws consent will always be asked about the reason(s) and the presence of any AE. If a subject withdraws from participation in the study, then his/her enrolment code cannot be reused. Withdrawn subjects will not be replaced.

3.7.3 Termination of the study

The study may be stopped if, in the judgment of AstraZeneca, trial subjects are placed at undue risk because of clinically significant findings that are not considered to be consistent with continuation of the study.

Regardless of the reason for termination, all data available for the subject at the time of discontinuation of follow-up must be recorded in the CRF (case report Form). All reasons for discontinuation of treatment must be documented.

In terminating the study, the Sponsor will ensure that adequate consideration is given to the protection of the subjects' interests.

3.7.4 Completion of the study

For subjects who received RP, it will be considered as completion of the study if the subjects completed the 3 months post-surgical follow-up period. If the subjects who actually can not receive radical prostatectomy within 30 days after 24 weeks neoadjuvant therapy, it will be considered as completion of the study and reason for failure to operate will be collected.

4 STUDY PLAN AND TIMING OF PROCEDURES

4.1 Study schedule

Visit	1	2	3	4	5 ^e	6	7	8 ^g	For
Day	-28 to -1	1	85	169/E nd of treatm ent	EOT+30	RP+30	RP+90	Study completio n/disconti nuation	details see Protocol Section
Visit window	_	±5d	±5d	±5d		±5d	±5d	±5d	
Written informed consent	X								4.2
Demographics	X								4.2
Physical examination	X	Xa							4.2
Medical/surgical history	X								4.2
Inclusion/exclusion criteria	X								4.2
ECOG performance status	X	Xa	X	X	Xª		X	X	4.2, 4.3 & 4.4
Vital signs, body weight	X	Xa	X	X	Xª		X	X	4.2
ECG	X	Xa			Xa				4.2
Imaging (CT or MRI)	x					X (clinical ly indicated)	X (clinical ly indicated)	X (clinical ly indicated)	4.2, 4.3 & 4.4
Bone scan	X								4.2, 4.3 & 4.4
Gleason score	X				X				4.2 & 4.4
Zoladex and Casodex treatment		Xc	Xc						4.3
RP evaluation				X					4.3
RP					X				4.4
Assessment after radical prostatectomy plus ePLND					X				4.4
ADT after RP						X ^b	Xb	X ^b	4.4

Visit	1	2	3	4	5°	6	7	8 ^g	For
Day	-28 to -1	1	85	169/E nd of treatm ent	EOT+30	RP+30	RP+90	Study completio n/disconti nuation	details see Protocol Section
Visit window	-	±5d	±5d	±5d		±5d	±5d	±5d	
Concomitant medication	X	X	X	X	X	X	X	X	4.2, 4.3 & 4.4
Adverse event	X	X	X	X	X ^d	X ^d	X ^d	X ^d	4.3 & 4.4
Haematology and clinical chemistry	X	Xa	X	X		X	X	X	4.2, 4.3 & 4.4
Blood germline forHRRm collected				X(all patien ts)					4.3
Tumor tissue for HRRm collected					X ^h				4.4
Urinalysis	X	Xa							4.2
Serum testosterone level	X	Xa	X	X		X	X	X	4.2, 4.3 & 4.4
Serum PSA level	X	Xa	X	X		X	X	X	4.2, 4.3 & 4.4

a. If assessed within 7 days before enrolment and meets the stated eligibility criteria (if applicable), it does not need to be repeated on Day 1 of study treatment unless investigator believes that it is likely to have changed significantly.

b. The treatment will be based on investigator's discretion

c. Casodex will be administrated till Week 24

d. AEs will be actively collected from ICF to 12 weeks after last dose of Zoladex

e. Radical prostatectomy should be performed within 30 days after end of NHT. The visit will be ended for the patients without radical operation following NHT after collection of the reason for failure to receive an operation.

f. The visit will be completed after follow-up for three months following radical operation

g. As withdrawal from the study is needed as required by the patient or judged by the investigator, the visit is ended prematurely. If relevant information has been collected 7 days prior to premature end of the visit, it does not need to be re-collected at the premature end of the visit, unless a possible significant change is considered by the investigator.

h. The tumor tissue for HRRm testing will be sent out to central lab within RP+30days

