4.4 Surgery and Post-surgical follow-up period

The ECOG performance status, vital signs, body weight, ECG, gleason score, RP, assessment after radical prostatectomy plus ePLND, adverse event, tumor tissue HRRm test will be collected on V5 (EOT+30days). The tumor tissue for HRRm testing will be sent out to central lab within RP+30days.

Radical prostatectomy should be performed for eligible subjects within 30 days after Day 169 /the end of treatment visit. The reason for failure to receive an operation will be collected for the patients without radical operation and a safety follow-up visit will be performed (12 weeks after the last dose of zoladex)

The tumor tissue for HRRm testing will be collected and sent out to central lab within 30 days after RP. All subjects receiving radical operation following NHT will be subject to evaluation of surgery related parameters as well as tumor tissue HRR mutation test after the operation. If scheduled study assessments cannot be obtained because of a holiday, these assessments should be obtained at the soonest following date, unless the soonest following date is not more than 2 days away from the evaluation time of other planned studies.

Descriptions of the procedures for this period are included in the Study Plan with exceptions of the following specific requirements for the follow-up period:

All visits must occur within \pm 5 days from the scheduled date starting at visit 5, unless otherwise noted. All assessments will be performed on the day of the specified visit unless a time window is specified.

ECOG performance status will be performed during post-surgical follow-up period, or at the study completion/discontinuation visit.

Haematology and Serum chemistry will be tested during post-surgical follow-up period (in RP+30 and RP+90) .

Serum PSA level and testosterone level will be analysed during post-surgical follow-up period, or at the study completion/discontinuation visit..

The visit will be terminated on,RP+90 days, the serum PSA level and testosterone as well as surgery associated complications will be collected.

Premature end of follow-up is needed as required by the patient or judged by investigator during follow-up, the ECOG performance status, hematology, serum chemistry, serum PSA, testosterone, concomitant medication and adverse drug reaction will be collected at the study completion/discontinuation visit.

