8.4 Outcome measures for analyses

8.4.1 Primary endpoint

Actual radical prostatectomy rate

Actual radical prostatectomy rate is defined as the rate of the subjects who perform radical prostatectomy within 30 days after end of NHT

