4.1.1 Visit window definition

For treatment period, all post-baseline visits before RP surgery must occur within \pm 5 days from the scheduled date, all regarding assessments should be performed within the specified time window.

Visit post radical operation should be conducted at 180 ± 10 . And if a subject chose not to conduct the RP surgery, the reason should be recorded at the same visit.

For post-surgical follow-up period, all visits must occur within \pm 5 days from the scheduled date. All assessments will be performed within the specified time window.

If multiple readings are recorded within a single visit window, please refer to the rules below.

• If there are 2 or more observations within the same visit window, then the non-missing 1 closest to the visit will be used in the analysis.

- If 2 observations are equidistant from the visit, then the non-missing observation with the earlier collection date will be used in the analysis. If 2 observations are collected on the same day, then the non-missing 1 with the earlier collection time will be included in the analysis.
- If 2 observations are collected on the same day with missing time, the more conservative record will be included in the analysis

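### The SAP dates the post-operation visit at Day 180 ± 10, which a Visit 5 at EOT+30 never meets, and protocol and SAP score an operation at EOT+31 to +35 in opposite ways

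*Protocol*

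**What the plan says.** **Protocol, timing.** The schedule in 4.1 puts Visit 4 at Day 169 ± 5 and Visit 5, which carries the radical prostatectomy (RP), at EOT+30. Footnote e to Visit 5 states "Radical prostatectomy should be performed within 30 days after end of NHT". Section 4.4 repeats the limit: "Radical prostatectomy should be performed for eligible subjects within 30 days after Day 169 /the end of treatment visit". The same section lists the operation among the items collected at that visit ("RP, assessment after radical prostatectomy plus ePLND, adverse event, tumor tissue HRRm test will be collected on V5 (EOT+30days"), and then applies a general tolerance of ±5 "days from the scheduled date starting at visit 5, unless otherwise noted".

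**Protocol, endpoint.** Section 8.4.1 counts the "rate of the subjects who perform radical prostatectomy within 30 days after end of NHT". Section 8.3 puts the same 30 days into the RP analysis set (RPAS). Section 5.1.1 defines the same rate with no time limit.

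**SAP, timing.** Section 4.1.1 says "Visit post radical operation should be conducted at 180" ± 10. If a subject chose not to have surgery, the reason is to be recorded at that same visit. Section 4.1 also gives Visit 4 the value 180 ± 10.

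**SAP, endpoint.** Sections 3.1 (primary endpoint) and 2.1 (RPAS) count anyone actually operated on after NHT and set no time limit. Section 6 declares no change from the protocol.

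**The concern.** Visit 5 holds the event that defines the primary endpoint, so its dates should agree wherever they appear. They disagree in two ways.

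First, the SAP window ends before the protocol's surgery period does. An operation that is on time under the protocol can fall outside the SAP window. Visits 4 and 5 also share one SAP window, although ECOG and vital signs are scheduled at both and summarised by time point. The reason for no surgery can fall due while the protocol still allows surgery.

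Second, a site could take the ±5 days to cover the operation and operate a few days after EOT+30. Whether that subject counts as a success, and whether his margin, node and staging results enter the RPAS tables, would depend on which document the programmer follows.

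**Working it through.** End of NHT is taken as the end of treatment visit (Visit 4), as SAP 4.1 equates the two.

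**1. The plan's own figure.** From protocol 8.2: rate 90%, half-width 6.1%, 95% interval, 10% dropout.
n = p(1 − p)(z/d)² = 0.90 × 0.10 × (1.96/0.061)² = 92.9, so 93.
93/(1 − 0.10) = 103.3, so 104.
The stated 104 is reproduced, and nothing below changes it.

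**2. Visit 5 against the SAP window.** SAP window: 180 − 10 = 170 to 180 + 10 = 190.

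| Visit 4 day | EOT+30 | Days past 190 | EOT+25 to +35 | Days of that range inside 170–190 |
|---|---|---|---|---|
| 164 | 194 | 4 | 189–199 | 2 |
| 165 | 195 | 5 | 190–200 | 1 |
| 169 | 199 | 9 | 194–204 | 0 |
| 174 | 204 | 14 | 199–209 | 0 |

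From Visit 4 on Day 166 onward the overlap is zero. No permitted Visit 4 day puts EOT+30 inside the SAP window.

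**3. Operations earlier in the 30 days.** With Visit 4 on Day 169, surgery may take place on Days 170 to 199.
- Days 170–190: 21 of 30 inside the SAP window.
- Days 191–199: 9 of 30 (30%) after it closes.

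At the edges of the Visit 4 window, 4 of 30 days (Visit 4 on Day 164: Days 191–194) or 14 of 30 days (Visit 4 on Day 174: Days 191–204) fall after it closes.

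**4. Visit 4 in the same window.** Of the permitted Visit 4 days 164–174, only 170–174 (5 of 11) lie in Days 170–190. The nominal Day 169 is one day outside. SAP 4.1 describes this point as 12 weeks after the last injection. With the last implant on Day 85, 85 + 84 = 169, not 180. SAP 4.1.1 keeps the observation closest to the visit. If both visits are windowed around Day 180, a Visit 4 record on Day 174 (6 days away) is chosen over a Visit 5 record on Day 187 (7 days away).

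**5. An operation at EOT+31 to +35.** Read literally, ±5 days around EOT+30 spans 11 days, of which 5 lie beyond the 30-day limit.

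| Text | Primary endpoint | RPAS |
|---|---|---|
| Protocol 8.4.1 / 8.3 | failure | out |
| Protocol 5.1.1 | success | – |
| SAP 3.1 / 2.1 | success | in |

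Each such operation changes the rate by 1/104 = 0.96 points. The documents give no count of operations or of late ones. As an illustration, assume a full analysis set of 104 with 94 operated on, k of them late and scored as failures. Intervals are Clopper-Pearson, as named in protocol 8.5.1.

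| k | Rate | 95% CI |
|---|---|---|
| 0 | 94/104 = 90.4% | 83.0 to 95.3 |
| 1 | 93/104 = 89.4% | 81.9 to 94.6 |
| 3 | 91/104 = 87.5% | 79.6 to 93.2 |
| 5 | 89/104 = 85.6% | 77.3 to 91.7 |

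Five late operations would move the rate by 5/104 = 4.8 points, against a planned half-width of 6.1.

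**The case against.** A reader might infer that the plan invites operations up to EOT+35 and then scores them as failures. The documents do not support that. The tolerance in 4.4 yields where something else is noted, and the same section and footnote e both limit the operation to 30 days. The better reading is that the limit governs. What stands is that 4.4 also lists the operation as a Visit 5 item and does not say that the tolerance leaves it untouched. The scoring as a failure belongs to protocol 8.4.1 alone. Under SAP 3.1 the shift in the primary rate is zero. That answers the charge of mis-scoring but exposes a contradiction between the two documents.

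A reader might also infer that Visit 5 data in general miss the SAP window. They do not: 30 days is an upper limit, and 21 of the 30 nominal surgery days fall inside.

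The remaining objections limit the damage:
- SAP 4.1.1 only chooses among several readings within a window. It has no rule that discards records outside one. The Visit 5 items affected are descriptive safety summaries or listings, and no primary or pathological endpoint is defined through the window.
- SAP 4.1.1 also applies ±5 days to visits before surgery, so a programmer might window Visit 4 correctly despite SAP 4.1. The SAP then holds two windows for one visit.
- The rule on recording the reason speaks of a subject who chose not to have surgery, and a refusal can be recorded at any time. Protocol 3.7.4 covers failure to operate within 30 days. The risk is therefore that a reason is closed too early, not that the text requires it.
- The empty window cell for Visit 5 in the schedule may come from the way the table was extracted. Nothing here rests on it.

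**Conclusion.** The point holds as a conflict of dates and of definitions, and the text is wrong as written.

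The window conflict needs no assumption beyond counting from Visit 4. A Visit 5 at EOT+30 misses SAP Days 170–190 by 4 to 14 days, and with Visit 4 on Day 169, 30% of the permitted surgery days fall after the window closes. Visit 4 and Visit 5 share that window, and the nominal Visit 4 is itself one day outside it.

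The scoring conflict is conditional on an operation taking place after EOT+30. If one does, protocol 8.3/8.4.1 and SAP 2.1/3.1 treat it in opposite ways, at 0.96 points each, while SAP section 6 declares no change. The figures for 94 operated and five late are assumptions that show scale, not forecasts. The planned 104 subjects and 6.1% precision are unaffected.

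**What to change.** - In SAP 4.1 and 4.1.1, replace Day 180 ± 10 with windows that match the protocol schedule. Give Visits 4 and 5 separate windows, with Visit 5 counted from EOT.
- In protocol 4.1 and 4.4, state that the ±5 days do not extend the limit for the operation, or state one common limit.
- Use that same limit in protocol 5.1.1, 8.3 and 8.4.1 and in SAP 2.1 and 3.1. If the two documents are meant to differ, say so in SAP section 6.
- Finalise the classification as not operated, and its reason, only once that interval has closed.

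The length of the interval is for the sponsor's clinical team; the requirement here is that the passages be reconciled. The cost is protocol and SAP wording, with no change to the sample size.

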4.2 Enrolment/screening period

Procedures will be performed according to the Study Plan. Written informed consent for participation in the study must be obtained before performing any study-specific screening tests or procedures.

At screening, consenting subjects are assessed to ensure that they meet eligibility criteria. Subjects who do not meet these criteria must not be enrolled in the study. Screening and pretreatment tests will be performed within 28 days preceding Day 1 (defined as the day of first dose of study drug). Results of standard of care tests performed prior to obtaining informed consent and within 28 days prior to study entry may be used; such tests do not need to be repeated for screening.

The study procedures carried out during this period include: demographics, physical examination, medical/surgical history, ECOG performance status, vital signs, body weight, ECG, Imaging (CT or MRI), bone scan, Gleason score, concomitant medication, haematology and clinical chemistry, urinalysis, serum testosterone level and PSA level. Results must be judged and confirmed by the investigator prior to study drug administration on Day 1.

4.3 Treatment period

Descriptions of the procedures for this period are included in the Study Plan with exceptions of the following specific requirements for the treatment period:

All visits must occur within \pm 5 days starting at visit 2 from the scheduled date. All assessments will be performed on the day of the specified visit unless a time window is specified.

ECOG performance status and weight will be performed at Day 1, Day 85, or Day 169/at end of treatment visit.

Haematology and Serum chemistry will be tested at Day 1, Day 85, or Day 169/at end of treatment visit. Additional monitoring for haematology and serum chemistry will be provided as clinically indicated.

Serum PSA level and testosterone level will be collected at Day 1, Day 85 or Day 169/at end of treatment visit.

Assessment of subject's eligibility for radical prostatectomy will be performed in all enrolled subjects by investigators at Day 169/at end of treatment visit as well as blood sample for germline HRR mutation testing of all enrolled subjects will be collected. If scheduled study assessments cannot be obtained because of a holiday, these assessments should be obtained at the soonest following date, unless the soonest following date is not more than 2 days away from the evaluation time of other planned studies.

If the information as the ECOG performance status, haematology, serum chemistry, serum PSA, testosterone, concomitant medications has been collected within one week prior to the end of treatment visit, it will no more be collected, unless it is considered by the investigator that relevant information will be significantly changed in a short period.

Investigators can suggest patients to take regular serum transaminase test in the outpatient department of hospital for the first four months of treatment with Casodex and then periodically, followed clinical practice or as clinical indicated. Management of abnormal results of serum transaminase that causally related to Casodex please follow the guidance in Section 6.10.

If the dose of Zoladex (Goserellin acetate implant) is delayed by more than 7 days during ontreatment period, early termination of study treatment will be considered. If Zoladex is permanently discontinued, Casodex should be permanently discontinued.

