6.10 Management of IP related toxicities

Laboratory abnormalities including elevated AST, ALT, bilirubin, BUN (blood urea nitrogen), and creatinine and decreased hemoglobin and white cell count have been reported in both Casodex-LHRH analogue treated and flutamide-LHRH analogue treated subjects.

Rare cases of death or hospitalization due to severe liver injury have been reported postmarketing in association with the use of Casodex. Hepatotoxicity in these reports generally occurred within the first three to four months of treatment. Hepatitis or marked increases in liver enzymes leading to drug discontinuation occurred in approximately 1% of Casodex patients in controlled clinical trials.

Serum transaminase levels should be measured prior to starting treatment with Casodex, at regular intervals for the first four months of treatment, and periodically thereafter. If clinical symptoms or signs suggestive of liver dysfunction occur (e.g., nausea, vomiting, abdominal pain, fatigue, anorexia, "flu-like" symptoms, dark urine, jaundice, or right upper quadrant tenderness), the serum transaminases, in particular the serum ALT, should be measured immediately. If at any time a subject has jaundice, or their ALT rises above two times the upper limit of normal, Casodex should be immediately discontinued with close follow-up of liver function.

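### Section 6.10 calls for regular transaminase tests in the first four months of Casodex, but 4.1 and 4.3 schedule one and leave the rest optional, with no interval

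*Protocol*

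**What the plan says.** Protocol section 6.10 sets the expectation: "Serum transaminase levels should be measured prior to starting treatment with Casodex, at regular intervals for the first four months of treatment". Later testing is to be periodic. It also sets the action: if a subject is jaundiced or "their ALT rises above two times the upper limit of normal, Casodex should be immediately discontinued". Liver function is then to be watched closely. Suggestive symptoms or signs call for an immediate ALT.

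Protocol section 4.3 sets the schedule: "Haematology and Serum chemistry will be tested at Day 1, Day 85, or Day 169/at end of treatment visit". The table in 4.1 marks all three of these visits, plus screening, and shows no visit between Day 1 and Day 85. The chemistry panel in 5.2.1 includes ALT and AST.

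On testing beyond the schedule, 4.3 says "Investigators can suggest patients to take regular serum transaminase test in the outpatient department of hospital for the first four months". How often this is done, and what happens later in treatment, is left to local practice or clinical need. It adds that "Additional monitoring for haematology and serum chemistry will be provided as clinically indicated". Section 5.2.1 is equally permissive about extra outpatient tests. Section 4.3 cites 6.10 once in this context: "Management of abnormal results of serum transaminase that causally related to Casodex please follow the guidance in Section 6.10". Neither 4.3 nor 6.10 gives an interval in weeks.

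**The concern.** Two parts of the protocol cover the same test, drug and months with different force. Section 6.10 says the testing should happen; 4.3 says it may be suggested. Someone running visits from 4.1 and 4.3 is sent to 6.10 only once an abnormal result exists, so the cross-reference does not lead to the testing expectation.

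This matters because 6.10 reports rare post-marketing deaths and admissions from severe liver injury on Casodex, and places hepatotoxicity mostly in the first three to four months. In a man without symptoms or jaundice, only a blood test can trigger the 2 x ULN stopping rule, and none is scheduled before Day 85. Whether he is tested sooner depends on which section his site works from, so detection may differ across the roughly 15 sites.

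**Working it through.** The plan gives no detection interval to reproduce, so the check is day arithmetic on the schedule.

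**Inputs**
- Day 1 is the day of first dose (Protocol 4.2).
- Scheduled on-treatment chemistry: Day 85 and Day 169 (4.1, 4.3).
- Visit window: ±5 days (4.1, 4.3), so Day 80 to 90 and Day 164 to 174.
- Casodex lasts 24 weeks (7.2): 24 × 7 = 168, so the nominal last dose is on Day 168.
- Four months: Day 113 if taken as 16 weeks, about Day 123 if taken as calendar months.

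**Scheduled on-treatment tests in the first four months.** Day 85 (80 to 90) falls inside on either reading. The next visit, at the earliest 169 − 5 = Day 164, falls outside. The count is 1.

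**Longest time an asymptomatic rise can go undetected on the schedule alone**

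| Situation | Calculation | Days |
|---|---|---|
| Rise just after first dose, visit on Day 85 | 85 − 1 | 84 |
| Rise just after first dose, visit on Day 90 | 90 − 1 | 89 |
| Rise just after a Day 85 test, next on Day 169 | 169 − 85 | 84 |
| Rise just after a Day 80 test, next on Day 174 | 174 − 80 | 94 |

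The last case still starts within the four months. Its 94 days are days undetected, not days on drug: with a nominal last dose on Day 168, exposure after such a rise is at most 168 − 80 = 88 days.

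**With a 4-weekly schedule (illustration).** For tests on Days 29, 57, 85 and 113, the longest nominal gap from Day 1 to Day 113 is 28 days. If two neighbouring visits fall at opposite ends of their windows, for example Day 24 and Day 62, it is 62 − 24 = 38 days.

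**Extra draws.** Days 29, 57 and 113 are new: 3 per subject, at most 3 × 104 = 312.

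**The case against.** The best reply is that nothing is missing. The scheduled chemistry is a minimum; neither 4.1 nor 4.3 forbids what 6.10 asks for, and 4.3 echoes the same four-month timetable. Section 6.10 is protocol text, and 9.2.4 bars unagreed deviation. Leaving the interval to local practice may be deliberate: 1.3 describes the combination as standard treatment with well-understood toxicity, and both drugs are marketed in China. Symptom-prompted ALT, jaundice and clinically indicated tests remain as safeguards. Exclusion criteria 8 and 10 and the review of results before Day 1 lower baseline liver risk.

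Much of this stands. A reader might infer that the two sections are irreconcilable, or that the protocol has no liver monitoring. The documents do not support either: a site can meet both sections by following 6.10, and symptomatic cases are covered.

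It does not close the gap for asymptomatic rises. If 6.10 binds, 4.3 presents a requirement as optional and needs correcting. Nor is the word *should* mere advice in this protocol: section 3 uses it for eligibility criteria that admit no exceptions. Entry screening cannot detect a rise that begins on Casodex. With no visit between Day 1 and Day 85, symptoms in that stretch reach the site only if the subject reports them. The documents give no reason for testing less than 6.10 describes.

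**Conclusion.** The mismatch is real and should be fixed. At a site that works from 4.1 and 4.3 as written, an asymptomatic ALT rise above 2 x ULN can go undetected for up to 84 days nominally, 89 from first dose with a Day 90 visit, and 94 in the Day 80 to Day 174 case. These are upper bounds. They assume that the rise starts just after a test or the first dose, that no symptoms or jaundice appear, and that no outpatient test is done.

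The number of subjects affected cannot be derived. A reader might apply the approximately 1% rate in 6.10 to 104 subjects (104 × 0.01 = 1.04) and conclude that about one case would be found late. That rate counts hepatitis or marked enzyme rises leading to discontinuation, however detected, and is given without a follow-up duration; it says nothing about delay. A reader might also infer that most of the liver risk has passed by Day 85. Section 6.10 gives no distribution of risk within the three to four months, so elapsed time cannot stand in for share of risk.

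The primary endpoint and sample size are unaffected: neither depends on how often transaminases are measured.

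**What to change.** In Protocol 4.3, replace the permissive wording so that investigators *should, per Section 6.10, arrange* the transaminase tests. Extend the cross-reference so that 6.10 governs testing as well as the management of abnormal results. State an interval for the first four months and show it in 4.1. One option is every 4 weeks (Days 29, 57, 85 and 113), at local or outpatient laboratories with results recorded. The documents give no interval, so this is a proposal and the sponsor should set the figure. No SAP change is needed.

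The cost is more than a wording edit. It means about 3 extra routine draws per subject. Days 29, 57 and 113 have no column in 4.1, so laboratory timepoints must be added there and in the data-capture system. Under 10.5 the amendment needs ethics committee approval before use, as does any resulting change to the consent form. Against that, 6.10 already calls for the testing, so the change aligns the schedule with an existing expectation.
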